#### Pre-dose ADA negative

- induced: ADA-positive sample post-baseline with ADA-negative sample at baseline (Treatment-induced ADA-positive subjects; for % the denominator is the number of subjects with ADA-negative sample at baseline)
  - Transient
  - Persistent

Overall ADA incidence (combined results of treatment-boosted and induced)

For induced ADA positive, summaries will also be provided based on the persistent or transient ADA status. The definition of persistent and transient is as follows.

Persistent ADA: a) Treatment-induced ADA detected at two or more sampling time points during the treatment (including follow-up period if any), where the first and last ADA-positive samples (irrespective of any negative samples in between) are separated by a period of 16 weeks or longer or b) Treatment-induced ADA incidence only in the last sampling time point of the treatment or follow up observation period\_or at a sampling time point within less than 16 weeks before an ADA-negative last sample.

Transient ADA: a) Treatment-induced ADA detected only at -one sampling time point during the treatment or follow-up observation period (excluding the last sampling time point) and that

For business use only

Page 29 of 41 CCSJ117A12201C

sampling point is 16 weeks or more before an ADA negative last sample or b) Treatmentinduced ADA detected at two or more sampling time points during the treatment (including follow-up period if any), where the first and last ADA-positive samples (irrespective of any negative samples in between) are separated by a period less than 16 weeks, and the subject's last sampling time is ADA Negative.

ADA titer kinetics will be summarized by treatment group with data reported as boxplot (titer range, Q1, Median (Q2), Q3, and outliers) of ADA titer at each time point for each treatment group up to Week 24. The plot will include total subjects, number of subjects with positive ADA, and % of subjects with positive ADA at each time point. Please see example below from Shankar et al.

[figure not shown]

Fig. 3. ADA titer kinetics. This plot of titers over time in a study is useful in determining whether the ADA levels tend to change over time during the treatment. Each *box plot* represents the titer range, Q1, Median (Q2), Q3, excluding outliers (*asterisks*)

Listings of all ADA titer values will be presented for all subjects by treatment group, subject, and visit/time and by study period. Samples collected at unscheduled visits will not part of the analysis. ADA titer values will be summarized as a table by treatment arm for ADA titer at each time point for each arm up to Week 24.

Systemic exposure of CSJ117 will be measured concomitantly with ADA levels for interpretation purposes. Systemic exposure data will be summarized and listed. No correlative analysis will be conducted.

Additional analyses might be performed to assess immunogenicity and may depend on emergent data from the study.

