Hematology	Х			X ⁸		X ⁸	X ⁸	X ⁸	X ⁸		Х		Х	Х
Clinical Chemistry	х			X ⁸		X ⁸	X ⁸	X ⁸	X ⁸		х		х	х

Period	Screenin g	В	aseline	9		Tr	eatme	nt			Follo	w up		
Visit Name	Screenin g ¹⁷	Run- In	Phon e visit	End of Run -In	Day 1	Wee k 2*	Wee k 4*	Wee k 8	Wee k 12	Week 14*	Wee k 16*	Wee k 20*	Wee k 24	PS W ^{1*}
Days	-42	-28	-14	1	1	15	29	57	85	99	113	141	169	-
Blood collection for ADA				X ⁸		X ⁸	X ⁸	X ⁸	X ⁸	х	х	х	х	х
PK Blood collection Pre- Dose				X ⁸		X ⁸	X ⁸	X ⁸	X ⁸	х	х	х	х	х
PK Blood collection Post- Dose 2hr ¹⁴					X ¹⁸									
PK Blood collection Post- Dose 4hr ¹⁴					X ¹⁸				X ¹⁸					
Contact IRT	S	S		S	S		S	S	S					S
CSJ117 Safety Extension Study participation discussion								S ¹³						
TB testing ¹⁵	S													

^X Assessment to be recorded in the clinical database or received electronically from a vendor

^s Assessment to be recorded in the source documentation only

¹ Premature Subject Withdrawal, no on site drug administration

² Optional, if needed

³ Only if Day 1 visit was postponed, due to repetition of spirometry or operational issue

⁴ Only for participating countries/sites

⁵ Patient has to be observed for at least 4 hours post-administration

⁶ If not achieved during the Run In visit, up to two additional attempts are allowed at separately scheduled visits before the End of Run in Visit. If reversibility is not demonstrated at Run in Visit and the two additional attempts, historical information may be used (Documented evidence of reversibility that was performed according to ATS/ERS guidelines (ATS/ERS 2019) within the 1 year prior to Screening).

⁷ Pre-dose regarding fluticasone/salmeterol

⁹ 3 hours post-dose

¹¹ To be confirmed by central lab if positive or indeterminate.

¹² Optional, only for consented patients

¹³ Latest at day 84. It can be conducted earlier.

¹⁴ In case a patient prematurely discontinued treatment but continued participation in the study, these PK samples will not be collected.

¹⁰ If ECG results are clinically abnormal, site has to repeat it twice and submit to the central reviewer

¹⁵ Where applicable by local regulations

¹⁶ Medication washout prior to spirometry training is not required

¹⁷ Screening visit can be optionally conducted across 2 days to collect laboratory samples and allow the laboratory evaluations including the blood eosinophil (EOS) counts first.

*Selected assessments for these visits could be performed off site

¹⁸ Within +/-15 minutes of specified sample collection time.

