#### 2.8.5.2 Subject ADA status

Any ADA sample collected beyond 150 days of the last dose of CSJ117 will not be used for summaries or derivations and will only be included in the listing.

Subject ADA status is defined as follows:

- *Treatment-induced ADA-positive subject*: subject with ADA-negative sample at baseline and at least one treatment-induced ADA-positive sample
- *Treatment-boosted ADA-positive subject*: subject with ADA-positive sample at baseline and at least one treatment-boosted ADA-positive sample
- *Treatment-unaffected ADA-positive subject*: subject with ADA-positive sample at baseline, no treatment-boosted ADA-positive samples, and at least one treatment-unaffected ADA-positive sample
- *Treatment-reduced ADA-positive subject*: subject with ADA-positive sample at baseline and at least one non-missing post baseline sample, all of which are ADA-negative samples
- *ADA-negative subject*: subject with ADA-negative sample at baseline and at least one non-missing post baseline sample, all of which are ADA-negative samples
- *Inconclusive subject*: subject who does not qualify for any of the above definitions or a subject for which the baseline sample is missing and CSJ117 PK concentration at the

time of ADA sample collection is > the drug tolerance level (10 microgram/mL) or missing

-Following data with number and percentage of subjects will be reported/tabulated by treatment group and during overall study duration. The following summaries of ADA subject status (n and %) will be provided using the *Immunogenicity incidence set* (for % the denominator is the number of subjects in the *Immunogenicity incidence set* unless otherwise specified). :

- ADA negative
- ADA positive (prevalence set)
  - Total ADA positive with no boost
- ADA inconclusive (exposure above drug tolerance according to validated method)
- Missing ADA data at pre-dose
- Missing ADA data at post-dose (Number of patients with atleast 1 missing sample)

Following data with number and percentage of subjects will be reported/tabulated by treatment group for the whole study period:

Pre-dose ADA positive

boosted: boosted is defined as ADA positive at pre-dose, and post dose titer values increase from pre-dose by more than 3-fold at any time point (Treatment-boosted ADA-positive subjects; for % the denominator is the number of subjects with ADA-positive sample at baseline)

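### SAP 2.8.5.2 gives no class to a treatment-induced patient with two or more ADA-positive samples less than 16 weeks apart who is still positive at the last sample

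*SAP*

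**What the plan says.** SAP 2.8.5.2 defines a treatment-induced patient as a "subject with ADA-negative sample at baseline and at least one treatment-induced ADA-positive sample". It then promises a further split: "For induced ADA positive, summaries will also be provided based on the persistent or transient ADA status". The split, set out under the pre-dose ADA-negative heading, has these limbs:

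- **Persistent (a):** two or more positive samples, where the first and last "ADA-positive samples (irrespective of any negative samples in between) are separated by a period of 16 weeks or longer".
- **Persistent (b), first part:** "Treatment-induced ADA incidence only in the last sampling time point of the treatment or follow up observation period".
- **Persistent (b), second part:** a positive "at a sampling time point within less than 16 weeks before an ADA-negative last sample".
- **Transient (a):** one positive sample that is not the last, 16 weeks or more before a negative last sample.
- **Transient (b):** two or more positives less than 16 weeks apart, where the patient's "last sampling time is ADA Negative".

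No third class or default is given. Protocol Table 8-1 (row "Blood collection for ADA") schedules a sample at the end of run-in and at Weeks 2, 4, 8, 12, 14, 16, 20 and 24, plus one at premature withdrawal. Under Protocol 9.2, a patient who enters the extension after the treatment period completes this study at Week 12.

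**The concern.** A positive last sample can be classed only by persistent (a), which needs a 16-week span, or by the first part of persistent (b), which needs that sample to be the only positive one. Every other limb needs a negative last sample. Repeated positives over a shorter span that run up to the last sample therefore fall between the limbs.

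The result runs against the purpose of the split. A patient positive only at Week 24 is persistent, while a patient positive at Weeks 12, 14, 16, 20 and 24 has no class. Further evidence of a sustained response takes the patient out of the persistent row. The two rows then need not sum to the treatment-induced total above them, and the persistent rate in an arm depends partly on when sampling ended.

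The inconclusive-subject category does not catch these patients. It covers a "subject who does not qualify for any of the above definitions", and they already meet the treatment-induced definition earlier in that list.

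**Working it through.** The plan gives no figure to reproduce. The check applies the limbs to every possible pattern of positive and negative samples.

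**Inputs.** Post-baseline ADA visits and study days are from Protocol Table 8-1: Weeks 2, 4, 8, 12, 14, 16, 20 and 24, which are Days 15, 29, 57, 85, 99, 113, 141 and 169. Baseline is negative, every sample up to the last is present and is either positive or negative, and spans use nominal weeks. The second part of persistent (b) is read as a single positive sample. With n visits there are 2^n − 1 patterns with at least one positive.

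**Last sample at Week 24** (2^8 − 1 = 255 patterns):

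| Class | Patterns | Count |
|---|---|---|
| Persistent (a), last positive at Week 24 | first positive at Week 2, 4 or 8: 64 + 32 + 16 | 112 |
| Persistent (a), last positive at Week 20 | first positive at Week 2 or 4: 32 + 16 | 48 |
| Persistent (b) | Week 24 only (1); single positive at Week 12, 14, 16 or 20 (4) | 5 |
| Transient (a) | single positive at Week 2, 4 or 8 | 3 |
| Transient (b) | two or more positives among the first seven visits (2^7 − 1 − 7 = 120), less the 48 above | 72 |
| No class | Week 24 positive, none at Weeks 2 to 8, at least one at Weeks 12 to 20: 2^4 − 1 | 15 |

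Total: 112 + 48 + 5 + 3 + 72 + 15 = 255. The unclassified patterns are exactly those with a first positive at Week 12, 14, 16 or 20 and a positive Week 24 sample. A patient first positive by nominal Week 8 and still positive at Week 24 is correctly persistent, because 24 − 8 = 16 weeks.

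**Last sample at Week 12** (2^4 − 1 = 15 patterns): the widest span is (85 − 15)/7 = 10 weeks, so neither persistent (a) nor transient (a) can be met. Persistent (b) takes 1 + 3 = 4 patterns, transient (b) takes 4, and 2^3 − 1 = 7 have no class (4 + 4 + 7 = 15). In this group only patients with a single positive sample can be persistent.

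**Other last samples**, by the same count: Week 14, 15 of 31; Week 16, 31 of 63; Week 20, 15 of 127.

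**Alternative reading of persistent (b).** If its second part covers any positive less than 16 weeks before a negative last sample, the no-class counts do not change, because they concern positive last samples. However, 72 − 4 = 68 of the 255 Week 24 patterns then meet both definitions. The 4 exceptions have all their positives at or before Week 8.

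**After the fix below.** Every positive last sample is persistent. With a negative last sample, a single positive is persistent if less than 16 weeks before it and transient otherwise; two or more positives are persistent if they span 16 weeks or longer and transient otherwise. These cases are exhaustive and do not overlap. Week 24: 180 persistent + 75 transient = 255. Week 12: 11 + 4 = 15.

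**The case against.** The best defence is that the intent is clear. Both transient limbs need a negative last sample, a lone positive last sample is already persistent, and only two rows sit under induced ADA, so a programmer would probably code any positive last sample as persistent. That is a fair reading of intent and it supports the fix. It still means disregarding the word *only*, and another programmer could leave these patients blank.

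The consequences are also small. SAP 1.2 and 2.8.5 report immunogenicity outside the CSR. SAP 2.8.5.2 plans no correlative analysis and lists all titers, and SAP 4 drops the analysis of ADA impact on efficacy and safety. This stands, and it sets the severity.

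A reader might infer more than the documents support:

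- **That sustained responses in general are lost.** They are not. With Week 24 data, onset by nominal Week 8 is classed correctly.
- **That early termination causes the gap.** It exists with full follow-up, and shorter sampling widens it. Week 12 is the end point only for patients who enter the extension directly after treatment; SAP 1.1 also allows entry after follow-up. The 8-week follow-up in SAP 1.1 ends at Week 20 only for patients who completed 12 weeks of dosing.
- **That many patients are affected.** Protocol 4.5 reports ADA in 13 of 15 CSJ117 patients in the earlier asthma study, but the documents give neither onset times nor the distribution of last samples.
- **That a one-day visit shift enlarges the gap.** Week 8 to 24 (169 − 57) and Week 4 to 20 (141 − 29) are each exactly 112 days. On actual dates, a span one day short would give 31 of 255 and 31 of 127. The SAP does not say which dates apply, but its wording by sampling time point and its exclusion of unscheduled samples favour nominal visits. This is missing detail and not an error.

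**Conclusion.** The rule is wrong as written, and the point is minor. A treatment-induced patient with two or more positives less than 16 weeks apart and a positive last sample has no class: 15 of 255 patterns with sampling to Week 24, and 7 of 15 when sampling ends at Week 12. The counts assume nominal weeks, complete sampling up to the last sample, and no inconclusive samples. They show which patterns are missed and not how often they occur, so no patient number is claimed.

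The effect is confined to the descriptive persistent/transient split. Overall ADA incidence, titer summaries, listings and the FEV1 analysis are unaffected.

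**What to change.** In SAP 2.8.5.2, reword persistent (b) in two places:

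1. First part: *ADA-positive at the last sampling time point, whether or not earlier samples were positive*.
2. Second part: *positive at a single sampling time point, less than 16 weeks before an ADA-negative last sample*.

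Define the last sample as the last conclusive one, positive or negative. SAP 2.8.5.1 also defines an inconclusive sample (assay negative, with drug concentration above the tolerance level or missing). Without this definition, a patient positive at Weeks 12 and 14 with an inconclusive Week 24 sample would still have no class.

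Two optional additions would help the reader: a sentence saying whether the 16 weeks are counted on nominal visits or actual dates, and a row giving, per arm, the number of treatment-induced patients by week of last ADA sample.

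The cost is two reworded phrases, one definition and a small derivation change. No patient contact is needed and the CSR is untouched.

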#### 1.1 Study design

This study is a phase IIb, multicenter, multi-national, double-blind, randomized, parallel-arm, placebo-controlled study to evaluate the effect of 5 dose levels of CSJ117 in adult subjects with inadequately controlled asthma despite medium to high dose ICS plus LABA.

The study will include:

- A screening period of approximately 2 weeks
- A single blinded placebo run-in period of 4 weeks (must be extended to 8 weeks for patients experiencing an asthma exacerbation or respiratory tract infection during the run-in period)
- A double blinded treatment period of 12 weeks
- A follow-up period of 12 weeks, study drug free, following the last dose of study drug. Or a follow-up period of 8 weeks for patients that discontinued the study due to early termination.

	Screening	Run-in			Treatment				Follow-up				
	30 3	•			- Fluticasone/Salmeterol 250/50 b.i.d OR 500/50 b.i.d**								
		Placebo Once daily			Placebo once daily CSJ117 0.5 mg once daily				Discontinuation of CSJ117				
					CS I11 / 1 mg once daily								
					CSJ117	2 mg once dai	ily						
				CSJ117 4 mg once daily									
					CSJ117	8 mg once dai	ily						
	2 weeks		4 weeks*				12 weeks				12 w	eeks	
Visit	Screening	Run-In	Phone Visit	End of Run-In	Day 1	Week 2	Week 4	Week 8	Week 12	Week 14	Week 16	Week 20	Week 24
Day	-42	-28	-14	1	1	15	29	57	85	99	113	141	169

Figure 1-1 Study design

or patients experiencing an asthma exacerbation during the run in perioc

\*\*depending on ICS-LABA entry dose

For business use only

At randomization, subjects will be stratified by their geographic region and blood eosinophil count (EOS) ( $\geq$  300 or < 300 cells/µl), measured at the screening visit. Approximately 52% of the total study population will be enrolled in the high EOS stratum. If recruitment for one EOS stratum is completed, only patients with baseline EOS count allowing randomization to the other stratum will be eligible. Subjects will be randomized in a 2:1:1:1:2:2 ratio to receive placebo or one of 5 doses of CSJ117 (0.5, 1, 2, 4, 8 mg) once daily for 12 weeks. All arms will have the same stratification ratio.

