#### 2.8.3 Laboratory data

Summaries of laboratory data will include on-treatment measurements, which are defined as measurements taken post-baseline but no later than 30 days after last dose of double-blind treatment for patients not entering the safety extension study (as described in Section 1.1) directly after the treatment period or not participating in the safety extension study. For patients entering the safety extension study directly after the treatment period, the on-treatment period lasts from the date of first administration of double-blind treatment to the date of the last actual administration of double-blind treatment.

For selected laboratory tests, the number and percentage of patients with newly occurring or worsening laboratory abnormalities meeting the clinically notable criteria at any time on-treatment, considering all on-treatment data from scheduled, unscheduled and premature discontinuation visits, will be summarized by laboratory parameter. Notable criteria are defined in Section 5.3.

Furthermore, the number and percentage of patients with newly occurring or worsening abnormalities in liver function tests (LFT) will be summarized by treatment and at any time on-treatment considering all on-treatment data from scheduled, unscheduled and premature discontinuation visit. LFT criteria are defined in Section 5.3.

The baseline value is the last value prior to first dose of double-blind treatment.

Laboratory data of patients with notable values will be listed.

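### The SAP drops unscheduled ADA samples without limiting this to by-visit summaries, so a patient whose only positive sample is unscheduled can be counted as ADA-negative

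*SAP*

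**What the plan says.** SAP 2.8.5.2 (Subject ADA status), in the text after the titer kinetics figure, says: "Samples collected at unscheduled visits will not part of the analysis". The sentence before it promises the opposite for listings: "Listings of all ADA titer values will be presented for all subjects". The sentence after it describes the titer table by time point.

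The subject classes in the same section depend on any single sample:

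- Treatment-induced: "subject with ADA-negative sample at baseline and at least one treatment-induced ADA-positive sample".
- ADA-negative: "subject with ADA-negative sample at baseline and at least one non-missing post baseline sample, all of which are ADA-negative samples".
- Inconclusive, as the residual class: "subject who does not qualify for any of the above definitions".

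None of these definitions is limited to scheduled samples. The headline measure is "Overall ADA incidence (combined results of treatment-boosted and induced").

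Elsewhere the SAP does the reverse. Any-time counts of notable laboratory values (2.8.3) are made "considering all on-treatment data from scheduled, unscheduled and premature discontinuation visits", and 2.8.4.1 and 2.8.4.2 do the same for QTcF and vital signs.

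Protocol 8.6.5.1 and Table 8-1 place ADA draws at the end of run-in, at Weeks 2, 4, 8, 12, 14, 16, 20 and 24, and at the premature-withdrawal (PSW) visit.

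**The concern.** An any-positive classification should use every valid sample. If a class of samples is removed first, a patient can meet the treatment-induced definition on the data collected and still be tabulated as ADA-negative. The SAP gives no reason for treating ADA differently from its other any-time safety counts.

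Immunogenicity is a secondary objective. In the earlier study in mild atopic asthma, 13 of 15 treated patients developed ADA (protocol 4.5). SAP section 4 removes the analysis of ADA impact on efficacy and safety, and 2.8.5.2 plans no correlative analysis. The status, incidence and titer summaries are therefore most of what will be reported, and their classification rule should be unambiguous.

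**Working it through.** The plan states no expected ADA incidence, so there is no figure to reproduce. The check applies the SAP definitions to patient patterns, with and without unscheduled samples, and then sizes the effect.

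**Step 1: classification.** The baseline is ADA-negative in every row.

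| Pattern | Scheduled post-baseline samples | Unscheduled sample | All samples used | Unscheduled dropped |
|---|---|---|---|---|
| 1 | All negative | Positive | Induced | ADA-negative |
| 2 | One inconclusive, rest negative | Positive | Induced | Inconclusive |
| 3 | None | Positive | Induced | Not in incidence set |
| 4 | None | Negative | ADA-negative | Not in incidence set |
| 5 | Any positive | Positive | Induced | Induced |
| 6 | Positive, or all negative | Baseline itself taken only at an unscheduled repeat visit | Induced, or ADA-negative | Not in incidence set |

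Patterns 3, 4 and 6 follow from SAP 2.8.5.1, where the incidence set needs both a baseline and a post-baseline sample. Pattern 6 is conceivable because protocol 6.3.2 allows an ad hoc randomization visit. The SAP does not say whether such a visit counts as unscheduled.

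**Step 2: direction.** With a scheduled baseline (patterns 1 to 5), dropping samples never creates a positive patient, so the count of incident positives stays the same or falls. The percentage is not so constrained. For illustration, take an arm of 74 (335 × 2/9 = 74.4) with 64 positives, a rate of 86.5% and close to 13/15 = 86.7%. One patient then gives:

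- pattern 1: 63/74 = 85.1%
- pattern 3: 63/73 = 86.3%
- pattern 4: 64/73 = 87.7%

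With 15 positives (15/74 = 20.3%) and three patients, pattern 1 gives 12/74 = 16.2% and pattern 4 gives 15/71 = 21.1%. The rates and the numbers of patients are assumptions.

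**Step 3: size per misclassified patient (pattern 1).** SAP 1.1 gives actual enrolment of 335 and allocation 2:1:1:1:2:2, which sums to 9 parts.

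- 0.5, 1 and 2 mg arms: 335/9 = 37.2, and 1/37.2 = 2.7 points.
- 4 and 8 mg arms: 2 × 335/9 = 74.4, and 1/74.4 = 1.3 points.

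These are minimum shifts. The SAP's denominators are the incidence set or, for induced ADA, subjects with a negative baseline. Neither can exceed the arm size.

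**Step 4: persistence.** Take a patient with a negative baseline who is positive at scheduled Week 4 and negative at every other scheduled visit, including Week 24, with an unscheduled positive between Weeks 20 and 24. If that sample counts, the first and last positives are at least 20 − 4 = 16 weeks apart and the patient is persistent. If it is dropped, the single positive lies 24 − 4 = 20 weeks before a negative last sample and the patient is transient.

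**The case against.** **Scope.** The sentence stands between the titer listing and the by-time-point titer table. When the SAP bars samples taken more than 150 days after the last dose, it names derivations as well as summaries; the unscheduled-visit sentence does not. It may have been meant for by-visit output only. This stands as a doubt about intent. It does not remove the problem, because the plain wording covers the whole analysis and sits in the subject-status section. A programmer could properly apply the filter to every status.

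**Number affected.** No unscheduled ADA draw is planned. There are up to eight scheduled post-baseline samples (four for patients who go straight into the extension), plus PSW. Patients who stop treatment are asked to keep attending. The number affected may be zero, and this stands.

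**Consequence.** All titers are listed, the analysis is descriptive, and it is reported outside the CSR. Scheduled-only ascertainment also gives patients more equal chances to test positive. These points limit the importance, but they do not justify labelling a patient with a valid positive as ADA-negative.

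**Stronger readings a reader might infer.**

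- *The excluded samples are mainly those drawn after reactions.* The documents do not support this. The hypersensitivity text in protocol 4.5 asks for no ADA draw. To characterise onset, protocol 8.6.5.1 relies on backup of earlier pre-dose PK samples.
- *Early termination turns many last samples into unscheduled ones.* SAP 1.1 adds "Or a follow-up period of 8 weeks for patients that discontinued the study due to early termination". Falling off a nominal week does not make a visit unscheduled, however. Protocol 9.1.4 treats terminated subjects as prematurely withdrawn, and PSW is a Table 8-1 visit that includes ADA.

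**Conclusion.** The point holds in a limited form. Applied as written, the exclusion can count a patient with a valid positive sample as ADA-negative, and it can change persistent or transient labels. The ADA-negative label requires a negative baseline and scheduled post-baseline samples that are all ADA-negative. Otherwise the patient becomes inconclusive, leaves the incidence set, or is positive anyway.

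A reader might conclude that reported incidence can only be understated. That is true only of the count of incident positives, and only with a scheduled baseline. The percentage can rise when ADA-negative patients leave the incidence set.

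The size is at least about 1.3 points per misclassified patient in the 4 and 8 mg arms and 2.7 points in the 0.5, 1 and 2 mg arms. This assumes that 335 patients split according to the allocation ratio. The number of such patients is not given and is probably small. The conclusion also assumes that the sentence governs subject status, which its wording allows but its position leaves uncertain. This is a cheap improvement.

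**What to change.** Replace the sentence in SAP 2.8.5.2 with wording to this effect: subject ADA status, persistence and ADA incidence use every non-missing sample within the 150-day cut-off, including PSW and unscheduled visits; only the by-visit tables and titer box plots are limited to scheduled visits. This matches the SAP's any-time counts for laboratory, QTcF and vital-sign data. Add a footnote to the status tables giving the number of patients whose status rests on an unscheduled sample alone.

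The cost is one SAP sentence, one footnote and a change to a programming filter. The downside is that patients with extra draws have slightly more chances to test positive, and the footnote shows how far this matters.
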